Attachment 1: Sample FACT-Leu (Version 4)

Below is a list of statements that other people with your illness have said are important. **Please circle or mark one number per line to indicate your response as it applies to the past 7 days.**

		PHYSICAL WELL-BEING	Not at all	A little bit	Some-what	Quite a bit	Very much
GP	1	I have a lack of energy	0	1	2	3	4
GP	2	I have nausea	0	1	2	3	4
GP	3	Because of my physical condition, I have trouble meeting the needs of my family.....	0	1	2	3	4
GP	4	I have pain	0	1	2	3	4
GP	5	I am bothered by side effects of treatment	0	1	2	3	4
GP	6	I feel ill	0	1	2	3	4
GP	7	I am forced to spend time in bed	0	1	2	3	4

		SOCIAL/FAMILY WELL-BEING	Not at all	A little bit	Some-what	Quite a bit	Very much
GS	1	I feel close to my friends.....	0	1	2	3	4
GS	2	I get emotional support from my family	0	1	2	3	4
GS	3	I get support from my friends	0	1	2	3	4
GS	4	My family has accepted my illness	0	1	2	3	4
GS	5	I am satisfied with family communication about my illness	0	1	2	3	4
GS	6	I feel close to my partner (or the person who is my main support)	0	1	2	3	4
Q1		Regardless of your current level of sexual activity, please answer the following question. If you prefer not to answer it, please mark this box and go to the next section.					
GS	7	I am satisfied with my sex life 	0	1	2	3	4

Please circle or mark one number per line to indicate your response as it applies to the past 7 days.

EMOTIONAL WELL-BEING

		No t at all	A little bit	Some- what	Quit e a bit	Very muc h
GE 1	I feel sad	0	1	2	3	4
GE 2	I am satisfied with how I am coping with my illness.....	0	1	2	3	4
GE 3	I am losing hope in the fight against my illness.....	0	1	2	3	4
GE 4	I feel nervous.....	0	1	2	3	4
GE 5	I worry about dying.....	0	1	2	3	4
GE 6	I worry that my condition will get worse.....	0	1	2	3	4

FUNCTIONAL WELL-BEING

		Not at all	A little bit	Some -what	Quite a bit	Very muc h
GF1	I am able to work (include work at home).....	0	1	2	3	4
GF2	My work (include work at home) is fulfilling	0	1	2	3	4
GF3	I am able to enjoy life	0	1	2	3	4
GF4	I have accepted my illness	0	1	2	3	4
GF5	I am sleeping well	0	1	2	3	4
GF6	I am enjoying the things I usually do for fun.....	0	1	2	3	4
GF7	I am content with the quality of my life right now.....	0	1	2	3	4

Please circle or mark one number per line to indicate your response as it applies to the past 7 days.

ADDITIONAL CONCERNS		Not at all	A little bit	Some- what	Quite a bit	Very much
BRM3	I am bothered by fevers (episodes of high body temperature).....	0	1	2	3	4
P2	I have certain parts of my body where I experience pain.....	0	1	2	3	4
BRM2	I am bothered by the chills	0	1	2	3	4
ES3	I have night sweats	0	1	2	3	4
LEU1	I am bothered by lumps or swelling in certain parts of my body (e.g., neck, armpits, or groin).....	0	1	2	3	4
TH1	I bleed easily.....	0	1	2	3	4
TH2	I bruise easily.....	0	1	2	3	4
HI12	I feel weak all over	0	1	2	3	4
BMT6	I get tired easily	0	1	2	3	4
C2	I am losing weight	0	1	2	3	4
C6	I have a good appetite.....	0	1	2	3	4
An7	I am able to do my usual activities	0	1	2	3	4
N3	I worry about getting infections	0	1	2	3	4
LEU5	I feel uncertain about my future health.....	0	1	2	3	4
LEU6	I worry that I might get new symptoms of my illness.....	0	1	2	3	4
BRM9	I have emotional ups and downs	0	1	2	3	4
LEU7	I feel isolated from others because of my illness or treatment	0	1	2	3	4

Attachment 2: Sample EQ-5D-5L

(English version for the UK)

SAMPLE

UK (English) v.2 © 2009 EuroQol Group. EQ-5D™ is a trade mark of the EuroQol Group

Under each heading, please tick the ONE box that best describes your health TODAY

MOBILITY

- I have no problems in walking about
- I have slight problems in walking about
- I have moderate problems in walking about
- I have severe problems in walking about
- I am unable to walk about

SELF-CARE

- I have no problems washing or dressing myself
- I have slight problems washing or dressing myself
- I have moderate problems washing or dressing myself
- I have severe problems washing or dressing myself
- I am unable to wash or dress myself

USUAL ACTIVITIES (e.g. work, study, housework, family or leisure activities)

- I have no problems doing my usual activities
- I have slight problems doing my usual activities
- I have moderate problems doing my usual activities
- I have severe problems doing my usual activities
- I am unable to do my usual activities

PAIN / DISCOMFORT

- I have no pain or discomfort
- I have slight pain or discomfort
- I have moderate pain or discomfort
- I have severe pain or discomfort
- I have extreme pain or discomfort

[figure not shown]
ANXIETY / DEPRESSION

- I am not anxious or depressed
- I am slightly anxious or depressed
- I am moderately anxious or depressed
- I am severely anxious or depressed
- I am extremely anxious or depressed

- We would like to know how good or bad your health is TODAY.
- This scale is numbered from 0 to 100.
- 100 means the best health you can imagine.
0 means the worst health you can imagine.
- Mark an X on the scale to indicate how your health is TODAY.
- Now, please write the number you marked on the scale in the box below.

YOUR HEALTH TODAY =

The best health
you can imagine

The worst health
you can imagine

Attachment 3: ECOG Performance Status Score

ECOG PERFORMANCE STATUS*	
Grade	ECOG
0	Fully active, able to carry on all pre-disease performance without restriction
1	Restricted in physically strenuous activity but ambulatory and able to carry out work of a light or sedentary nature, e.g., light house work, office work
2	Ambulatory and capable of all selfcare but unable to carry out any work activities. Up and about more than 50% of waking hours
3	Capable of only limited selfcare, confined to bed or chair more than 50% of waking hours
4	Completely disabled. Cannot carry on any selfcare. Totally confined to bed or chair
5	Dead

* As published in Am. J. Clin. Oncol.:

Attachment 4: Anticipated Events**Anticipated Event**

An anticipated event is an adverse event (serious or non-serious) that commonly occurs as a consequence of the underlying disease or condition under investigation (disease related) or background regimen.

For the purposes of this study the following events will be considered anticipated events:

Disease Based:

- Thrombocytopenia
- Anemia
- Febrile neutropenia
- Leukopenia
- Pneumonia
- Sepsis
- Urinary tract infection
- Broncopneumonias
- Bacteremia
- Pyrexia
- Asthenia
- Fatigue
- Dyspnea
- Cardia dysrhythmias (i.e., atrial fibrillation)

Population Based:

- Congestive heart failure

Reporting of Anticipated Events

All adverse events will be recorded in the CRF regardless of whether considered to be anticipated events and will be reported to the sponsor as described in Section 12.3.1, All Adverse Events. Any anticipated event that meets serious adverse event criteria will be reported to the sponsor as described in Section 12.3.2, Serious Adverse Events. These anticipated events are exempt from expedited reporting as individual single cases to Health Authorities. However if based on an aggregate review, it is determined that an anticipated event is possibly related to study drug, the sponsor will report these events in an expedited manner.

Anticipated Event Review Committee (ARC)

An Anticipated Event Review Committee (ARC) will be established to perform reviews of pre-specified anticipated events at an aggregate level. The ARC is a safety committee within the sponsor's organization that is independent of the sponsor's study team. The ARC will meet to aid in the recommendation to the sponsor's study team as to whether there is a reasonable possibility that an anticipated event is related to the study drug.

Statistical Analysis

Details of statistical analysis of anticipated events, including the frequency of review and threshold to trigger an aggregate analysis of anticipated events will be provided in a separate Anticipated Events Safety Monitoring Plan (ASMP).

INVESTIGATOR AGREEMENT

I have read this protocol and agree that it contains all necessary details for carrying out this study. I will conduct the study as outlined herein and will complete the study within the time designated.

1. INTRODUCTION

The purpose of this statistical analysis plan (SAP) is to describe the procedures and the statistical methods that will be used to analyze and report results for study JNJ-56022473-AML-2002.

JNJ-56022473-AML-2002 is an open-label, 2-part, multicenter, Phase 2/3 study to evaluate the safety and clinical efficacy of a combination of decitabine and talacotuzumab (JNJ-56022473) in subjects with acute myeloid leukemia (AML) who are suitable for experimental therapy (Part A) and in subjects with untreated AML who are not eligible for intense induction chemotherapy or hematopoietic stem cell transplantation (Part B).

2. STUDY ENDPOINTS

2.1. Primary Endpoints

Part A: Safety

Part B: Complete Remission (CR) rate and overall survival (OS)

2.2. Secondary and Exploratory Endpoints (Part B)

Secondary endpoints to be summarized in the clinical study report include the following:

- Event-free survival (EFS), defined as the time from randomization to treatment failure, relapse from CR or CR with incomplete blood count recovery (CRi), or death from any cause, whichever occurs first. Treatment failure is defined as >25% absolute increase in the bone marrow blast count from baseline to the present assessment.
- Overall response rate (ORR, CR + CRi)
- Rate of CR plus minimal residual disease (MRD) negative CRi
- Time to response, defined for subjects who achieved a best response of CR or CRi as time from randomization to achieving the best response
- Duration of response, defined for subjects who achieved a best response of CR or CRi as time from achieving CR or CRi to relapse
- MRD negativity
- Patient-reported outcomes (PROs) using the FACT-Leu (FACT-Leu Subscale, Trial Outcome Index, Physical Function, Functional Well-being, FACT-Leu Total Score, Emotional Well-being, Social/Family Function) and EQ-5D-5L (index score and Visual Analogue Scale [VAS] score).
- Safety

Transfusion frequency will be an exploratory endpoint to be summarized in the clinical study report.

3. SUMMARY OF STUDY DESIGN

Part A:

Six subjects will be enrolled in Part A and receive 1 dose of talacotuzumab at 9 mg/kg on Day 1 as a 180-minute IV infusion. Dose-limiting toxicities (DLTs) will be assessed during the DLT evaluation period (Cycle 1; 14 days).

Pharmacokinetic and pharmacodynamic assessments will be conducted during the 8-day talacotuzumab evaluation period. Upon completion of dosing, there will be a review of all available study data by a Study Evaluation Team (SET) to confirm the recommended phase 2 dose of 9 mg/kg talacotuzumab.

Subjects in Part A will continue on study (remaining in Part A) and start subsequent cycles of the combined study therapy with decitabine until treatment failure, relapse from CR/CRi, or death.

Part B:

Upon confirmation of the recommended phase 2 dose in Part A, Part B of the study will start. Subjects will be randomized in a 1:1 ratio to receive either decitabine + talacotuzumab or decitabine alone. Randomization will be stratified by baseline ECOG performance status (0-1 versus 2) and type of AML (de novo versus secondary).

In addition to evaluations by investigators, disease status will also be centrally reviewed and determined by an Independent Review Committee (IRC) in a blinded fashion.

Part B of the study will have 3 interim analyses. The first interim analysis will occur after approximately 80 subjects (40 subjects per arm) have been randomized and followed for at least 4 months. Guided by predefined statistical criteria based on CR and CR+CRi rates, the study will either continue enrollment to the full pre-specified Phase 3 sample size of 400 subjects or discontinue enrollment. The statistical criteria to guide the decision making will be based on the difference (Δ) in response rates between the 2 treatment arms (decitabine + talacotuzumab minus decitabine alone) as the following:

- If $\Delta\text{CR} \geq 15\%$ or $\Delta(\text{CR}+\text{CRi}) \geq 25\%$, then the study may continue enrollment to 400 subjects
- If $\Delta\text{CR} < 15\%$ and $\Delta(\text{CR}+\text{CRi}) < 25\%$, then the study may stop enrollment at approximately 120 subjects

EFS and available safety, PK, PD, MRD, and biomarker data will also be reviewed at the time of this first interim analysis.

If the enrollment continues to 400 subjects (approximately 200 subjects per arm), the pre-specified design elements are:

- A second interim analysis will occur after 160 subjects (approximately 80 subjects per arm) have been randomized and followed for at least 4 months; this is the final analysis for CR rate and the first interim analysis for OS. The study will not be stopped on the basis of the CR rate results.
- A third interim analysis (ie, the second interim analysis of OS) will be conducted when 180 deaths have occurred.

- The final analysis of OS will take place when 270 deaths have occurred.

If the study stops enrollment after the first interim analysis based on the pre-specified criteria, it is expected that approximately 120 subjects will have been randomized. These subjects will continue to be followed. The clinical cutoff in this case will be when 90 EFS events have occurred.

Overall type I error of 0.05 (2-sided) will be allocated between the 2 primary endpoints CR rate and OS using a gate keeping procedure as described below:

- There will be a formal statistical testing for superiority for CR rate at the first interim analysis of 80 subjects with 2-sided $\alpha=0.001$. The final analysis of CR rate (in terms of formal statistical hypothesis testing) will take place after 160 subjects have been randomized and followed for at least 4 months (to occur at the same time as the 1st interim analysis of OS) with 2-sided $\alpha=0.009$. The study and collection of response data continue after the final CR analysis regardless of the outcome of the analysis.
- Overall 2-sided $\alpha=0.04$ for OS; if the final analysis of CR rate achieves statistical significance, then $\alpha=0.009$ allocated to this CR analysis can be reclaimed by the OS analysis, ie, OS can be tested at the overall level of 0.049.
- The 2 interim analyses and final analysis for OS will utilize the O'Brien-Fleming α -spending procedure.

Statistical inferences including efficacy stopping boundaries (in terms of nominal α -value) for all planned interim and final analyses (2 primary endpoints, CR rate and OS) are shown in Table 1.

Table 1: Overall Statistical Inference

Analysis	Description	Clinical Cutoff	2-Sided α
IA.1	CR and CR+CRi	4 months after 80 subjects (40/arm) are randomized	0.001
IA.2	CR final analysis	4 months after 160 subjects are randomized	0.009
	OS interim analysis No. 1		0.0002
IA.3	OS interim analysis No. 2	180 deaths	0.0088 / 0.0116 ^a
Final ^b	OS final analysis	270 deaths	0.0372 / 0.0454 ^a
^a If CR rate reaches statistical significance.			
^b Final analysis will be carried out by Sponsor.			

An Independent Data Monitoring Committee (IDMC) will be established to evaluate safety and conduct the planned efficacy interim analyses. Upon completion of the first interim analysis, the IDMC requested a futility analysis of OS at the time of the second interim analysis. Survival data at the time of the second interim analysis will include approximately 100 deaths, which is 37% of the total 270 deaths planned at the final analysis. The futility boundary, in terms of the observed hazard ratio, is chosen to be 0.95. If the observed hazard ratio at the time of the secondary interim analysis is ≥ 0.95 , the OS result will be considered futile. Detailed characteristics of the futility criterion are described in a separate IDMC statistical analysis plan. This futility analysis was not pre-planned in the study protocol, hence is considered ad hoc.

The OS outcome met the futility criteria at the time of the second interim analysis; thereafter upon IDMC's recommendation, patient recruitment was terminated, treatment with talacotuzumab was discontinued, and treatment with decitabine may continue.

Analyses described in this document include all data from all randomized subjects up to the clinical cutoff that is defined as 6 months after the last subject was randomized.

4. DETERMINATION OF SAMPLE SIZE – STUDY PART B

The first interim analysis to guide the decision for study continuation will occur after approximately 80 subjects (approximately 40 subjects per arm) have been randomized and followed for at least 4 months. The operating characteristics of the criteria are shown in Table 2.

Table 2: Study Continuation Decision Rule, Operating Characteristics

Sample size	40/arm
Enrollment may continue to approximately 400 subjects	$\Delta CR \geq 15\%$ or $\Delta(CR+CRi) \geq 25\%$
Enrollment may stop with approximately 120 subjects	$\Delta CR < 15\%$ and $\Delta(CR+CRi) < 25\%$
False positive error rate ^a	0.04
False negative error rate ^b	0.10

^a Decision for enrollment to approximately 400 subjects, assuming true effect of decitabine alone and decitabine+talacotuzumab are the same: CR=15%, CR+CRi=25%

^b Decision for stopping enrollment with approximately 120 subjects, assuming true effect of decitabine alone: CR=15%, CR+CRi=25%, and true effect of decitabine+talacotuzumab: CR=40%, CR+CRi=55%

Δ =difference in response rate, decitabine+talacotuzumab minus decitabine alone

If the study continues enrollment to 400 subjects, both primary endpoints (CR rate and OS) will be powered for 80% with overall α allocation of 0.01 and 0.04, respectively (Table 3).

If the study stops enrollment after the first interim analysis it is expected that approximately 120 subjects would have been randomized to the study. In this case, the primary focus will be exploratory to assess if there is a clinically relevant improvement in EFS for decitabine + talacotuzumab-treated subjects compared with subjects treated with decitabine alone. Assuming median EFS of 4 months for the decitabine alone arm, an improvement of 2.8 months in the talacotuzumab + decitabine arm (or hazard ratio HR=0.59) is considered clinically meaningful. For this purpose, 90 EFS events will provide 80% power to rule out a HR=1.0 (no difference in EFS between the 2 treatment arms) using a 90% confidence interval.

Overall power and sample size determinations are summarized in Table 3.

Table 3: Sample Size Determination

Endpoint(s)	Effect Size, Decitabine+Talacotuzumab vs. Decitabine alone		Overall 2-side α	Total No. of Events	Total Sample Size
		Power			
Primary: CR Rate	40% vs. 15%	80%	0.01		160
Primary: OS	Median 11.4 vs. 8.0 months Hazard ratio=0.70	80%	0.04	270	400
Secondary: EFS	Median 6.8 vs.4.0 months Hazard ratio=0.59	80%	90% CI ^a	90	120

^a If enrollment stops with approximately 120 subjects, analysis of EFS is exploratory with hazard ratio estimate and corresponding 90% confidence interval (CI).

5. GENERAL DESCRIPTIONS AND DEFINITIONS

5.1. Summaries of Part A Data

Safety data from Part A of the study will be summarized descriptively and separately from Part B data.

5.2. Subject Populations (Part B)

Intent-to-Treat (ITT): All subjects randomized into the study, grouped per treatment assigned by randomization, regardless of the actual treatment received. ITT will be used for summaries of disposition, demographics, baseline disease characteristics, and all efficacy analyses unless specified otherwise.

Upon early termination of study recruitment after the second interim analysis, subjects' disease status is no longer assessed by the IRC. For analyses of endpoints that depend on IRC assessment, only subjects in the ITT population who had IRC assessment will be included. Subjects who died before having data for IRC review will be included.

Per-Protocol (PP): Subjects in the ITT population who received at least 1 complete dose of decitabine for the decitabine alone arm and at least 1 complete dose of talacotuzumab for the decitabine + talacotuzumab arm and have no major protocol deviations in terms of study entry criteria that by clinical judgement will have a potential to impact efficacy outcomes (see Section 6.6). The per-protocol population will be used for sensitivity analyses of the primary efficacy endpoints CR rate and OS.

For analyses of endpoints that depend on IRC assessment, only subjects in the PP population who had IRC assessment will be included. Subjects who died before having data for IRC review will be included.

Safety: All randomized subjects who received at least one dose of study medication, grouped according to actual treatment received. This population will be used for all summaries of safety and study drug exposure.

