Safety reviews will be performed in Part A and Part B. The safety assessments in Part A will occur prior to the initiation of Part B. This will include safety and available PK and PD data from single-agent talacotuzumab and the preliminary safety of the combination of decitabine + talacotuzumab. A Study Evaluation Team (SET) will monitor safety and study conduct on an ongoing basis during Part A of the study.

An Independent Data Monitoring Committee (IDMC) will be established to evaluate safety and efficacy data collected during Part B of the study as described in Section 3.1.

In addition to evaluations by investigators, disease status will be reviewed and determined by independent central review in a blinded fashion. Disease status based on independent central review will be the primary source for efficacy analyses.

After review of the data from Interim Analysis #2, the IDMC informed the Sponsor that the futility criterion for OS was met and that the CR rate did not meet per-protocol defined statistical significance. Given the lack of efficacy advantage of talacotuzumab + decitabine versus decitabine alone, the incidence of infusion-related reactions, and the complexities with premedications for drug administration, the benefit/ risk ratio is not favorable to continue treatment with talacotuzumab. The IDMC recommended closure of enrollment to the study and that subjects receiving talacotuzumab + decitabine should discontinue talacotuzumab treatment and may continue decitabine alone, according to Principal Investigator decision and subject agreement. All subjects will continue to be followed for survival and subsequent anti-cancer therapy. During the treatment phase with decitabine, subjects will be monitored for serious adverse events.

The end of study data collection is defined as when 270 deaths have occurred or 6 months after the last subject is enrolled, whichever occurs first. At that time, follow up of subjects will end. Subjects who are continuing to derive benefit from decitabine treatment as assessed by their investigator may continue to receive decitabine; during this period, only serious adverse events will be monitored and entered into the Company safety repository as described under Amendment 7.

SUBJECT POPULATION

Part A

Key eligibility criteria include the following: subjects diagnosed with AML according to the World Health Organization (WHO) 2008 classification system fulfilling all of the following criteria:

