11.1. Subject Information

The primary analysis population will be the all-randomized population, which will include all subjects in Part B. Safety will be evaluated for all subjects who have received at least 1 dose of study drug in Part A or Part B. The pharmacokinetic analyses will be performed on the pharmacokinetic evaluable population. Continuous variables will be summarized using descriptive statistics such as mean, standard deviation, and range. Categorical variables will be summarized using frequency tables.

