6.7.2.6. Minimal Residual Disease

The following analyses will be performed for MRD by treatment arm:

- For subjects who achieve CR, CRi, or MLFS, respectively, number and percent of subjects who achieve MRD negativity at time of achieving the response or at any time during the response
- For all subjects of the ITT population, number and percent of subjects who achieve MRD negativity at the time of achieving CR or CRi, or at any time during CR or CRi. Subjects who do not achieve CR or CRi will be considered MRD positive in these analyses. Analyses similar to those for CR rate will be performed.

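### SAP 5.2 counts a subject never reviewed by the IRC in the final response rates if that subject died, and drops the subject if alive

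*SAP*

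**What the plan says.** Protocol 11.1 states: "The primary analysis population will be the all-randomized population, which will include all subjects in Part B". SAP 5.2 also makes ITT the default for efficacy. SAP 3 says that its analyses cover "all data from all randomized subjects up to the clinical cutoff that is defined as 6 months after the last subject was randomized".

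SAP 5.2 then makes an exception because the IRC stopped assessing disease status once recruitment ended. For IRC-dependent endpoints, "only subjects in the ITT population who had IRC assessment will be included. Subjects who died before having data for IRC review" are included as well. The per-protocol paragraph repeats the restriction ("only subjects in the PP population who had IRC assessment will be included") and the same add-back for deaths. No sentence in either document restores a living subject without an IRC assessment. The SAP does not say how the added deaths are scored; non-response is implied.

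SAP 5.9 makes IRC status the primary source and adds an investigator-based analysis. SAP 6.7.2.2 and 6.7.2.3 analyse CR+CRi and CR plus MRD-negative CRi in the same way as CR, so all three rates inherit the rule.

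**The concern.** Take two subjects randomised shortly before IRC review ended. Neither is reviewed, and for the same administrative reason. If one dies, that subject counts, presumably as a failure; if the other lives, that subject disappears. Membership of the analysis set is decided by something that happens after randomisation and may differ between arms.

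Keeping early deaths as non-responders is sound in itself. The defect is that their equally unreviewed living peers are removed. CR is a primary endpoint and IRC is its primary source, so the headline response rates in the final report would rest on a denominator that a reader can neither reconstruct nor correct.

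**Working it through.** **Plan's own figure.** SAP 5.2 states no number. The nearest is the CR sample size in SAP 4 (40% versus 15%, overall two-sided alpha 0.01, 80% power, 160 subjects). It reproduces: Fisher's exact power at 80 per arm is 80.8%, and the continuity-corrected total is 162.

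**Inputs.** From the SAP: control CR 15%; median OS 8.0 months (control) and 11.4 months (combination). Assumed, because the documents give no counts: T = 150 per arm; N = 9, 25 or 35 late-randomised, never-reviewed subjects per arm; exponential survival; follow-up f to death. The wording of the add-back allows two readings:
- narrow: only deaths before the first marrow, f about 2 months;
- broad: any death up to cutoff. Cutoff is 6 months after the last randomisation, so f is about 6 to 8 months for late subjects.

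The N = 9 case comes from the EFS planning rate in Protocol 11.3: 120/15 = 8 per month, times 66/30.4375 = 2.17 months, gives 17.3 in total or 8.7 per arm.

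**Formulas.** Share dead: d = 1 − exp(−ln 2 × f/m). With m = 8.0, d = 0.159, 0.405, 0.455 and 0.500 at f = 2, 6, 7 and 8. Let A = T − N be the earlier subjects, R = 0.15 × A the responders, and E the living earlier subjects without IRC data.
- SAP rule: R/(A − E + N × d)
- Set defined by randomisation date: R/A = 15%
- All-randomised, no IRC data = non-responder: R/T

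**Control CR with E = 0:**

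| N | f = 2 (narrow) | f = 6 | f = 7 | f = 8 | R/T |
|---|---|---|---|---|---|
| 9 | 14.85% | 14.62% | 14.58% | 14.54% | 14.1% |
| 25 | 14.54% | 13.88% | 13.75% | 13.64% | 12.5% |
| 35 | 14.31% | 13.35% | 13.18% | 13.02% | 11.5% |

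Example, N = 25, f = 8: 18.75/(125 + 12.5) = 13.64%. Against 15%, the narrow reading lowers the rate by 0.15 to 0.69 points and the broad reading by 0.38 to 1.98.

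**Opposing effect.** Living earlier subjects without IRC data (withdrawn, lost, no usable sample) would ordinarily count as non-responders. Dropping them raises the rate. The two effects cancel at E = N × d: 1.4 to 5.6 subjects per arm on the narrow reading, 3.6 to 17.5 on the broad one. E is not in the documents, so the sign of the net bias is not either.

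**Arm difference from mortality alone** (true CR 15% in both arms, E = 0, broad reading): at medians of 11.4 and 8.0 months it is 0.09–0.10 (N = 9), 0.26–0.29 (N = 25) and 0.37–0.41 points (N = 35). At an OS hazard ratio of 0.95 it is about 0.01, 0.04 and 0.06. Equal mortality gives zero.

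**Do the assumptions fit together?** Not entirely. At 8 per month, 160 subjects plus 4 to 6 months of accrual gives 192 to 208 in total, not 300; reaching 300 needs (300 − 160)/6 to (300 − 160)/4, or about 23 to 35 per month. With E = 0, however, the rate depends only on the share N/T, which is 6% to 23% above. At 8 per month and about 100 per arm the share is 9/100 = 9%. At 25 per month it is 2.17 × 25/2 = 27 of 150, or 18%. Both lie inside the range shown.

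**The case against.** **The add-back is a sensible early-death rule.** A subject who dies before the first marrow is a known non-responder and should not be lost. That is correct, and this narrow reading is natural. A reader might infer that any death up to cutoff qualifies; the text does not settle this. Membership still depends on vital status on the narrow reading, with a smaller effect.

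**Little depends on it.** This largely stands. The formal CR analysis came at the second interim ("A second interim analysis will occur after 160 subjects (approximately 80 subjects per arm) have been randomized and followed for at least 4 months"), before IRC review stopped, and the protocol reports that "the futility criterion for OS was met and that the CR rate did not meet per-protocol defined statistical significance". It would be wrong to infer that the rule undermines that test or the OS result. The investigator-based analysis is a partial check, though Protocol Table 1C lists no disease evaluations after Amendment 6.

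**The departure is disclosed.** SAP 5.2 applies ITT unless otherwise specified, and protocol section 11 defers details to the SAP. Disclosure does not remove selection on outcome.

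**SAP 6.7.2.6 is not a clear contradiction.** It reads "For all subjects of the ITT population, number and percent of subjects who achieve MRD negativity at the time of achieving CR or CRi" and adds "Subjects who do not achieve CR or CRi will be considered MRD positive in these analyses". Taken literally, a living unreviewed subject is a failure there and absent from the CR table. But MRD negativity at CR or CRi itself depends on IRC status, so 5.2 may govern. This needs one clarifying sentence; it is not a proven conflict.

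**Conclusion.** The concern holds as a minor one. On either reading of the death clause, the denominators for the final IRC-based CR, CR+CRi and CR plus MRD-negative CRi rates depend on survival and are not the all-randomised population, in both the ITT and per-protocol sets.

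Under the stated assumptions, kept late deaths alone lower control CR by about 0.15–0.7 points (narrow) or 0.4–2 points (broad). The mortality-driven arm difference is about 0.1–0.4 points at the planned OS medians and under 0.1 at a hazard ratio of 0.95. The latter is closer to what is known, since SAP 3 sets futility at an observed hazard ratio of 0.95 or more and reports that it was met.

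A reader might infer that the rule inflates CR or favours one arm. The documents do not support this: the two effects oppose each other, and neither the number never reviewed nor the number of living subjects dropped is given. EFS falls under the same wording in 5.2, but no effect on EFS is shown here.

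**What to change.** In both paragraphs of SAP 5.2, define the IRC-evaluable set by one stated randomisation date relative to the date IRC review stopped, regardless of survival. Count subjects in the set without IRC data as non-responders.

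The plan's own 4-month minimum follow-up is the safer cut. The earliest workable cut is 66 days (Cycle 2 Day 28 = day 56, plus the 7-day window, plus up to 3 days from randomisation to first dose), but it leaves no room for cycle delay or central-review turnaround. It would also miss more late responses: Protocol 3.1 cites a median time to response of 4.3 months in an earlier decitabine study.

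Also:
- add an all-randomised sensitivity table, no IRC data = non-responder, labelled conservative;
- report never-reviewed and excluded subjects by arm and vital status;
- state that 6.7.2.6 uses the same set.

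**Cost.** SAP wording, one derivation and the added tables. Some late-randomised subjects with real IRC data leave the main table. A 4-month cut drops 4 − 2.17 = 1.83 months of accrual more than a 66-day cut: about 15 subjects in total at 8 per month, or about 46 at an assumed 25 per month. The all-randomised table is biased downward, as the R/T column shows.
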